3.1.2. Incidence of AEs and SAEs leading to discontinuations

The definition of a serious adverse event is described in Appendix 3 of the protocol.

A participant who discontinues study intervention due to an AE or an SAE will be flagged.

3.1.3. Incidence of clinically significant abnormal laboratory values and vital signs.

3.1.3.1. Laboratory Data

The investigator must review the laboratory report, document this review, and record any clinically significant changes occurring during the study in the AE section of the CRF. Clinically significant abnormal laboratory test findings are those that are not associated with the underlying disease, unless judged by the investigator to be more severe than expected for the participant's condition.

To determine if there are any clinically significant laboratory abnormalities, the hematological and clinical biochemistry and other safety tests will be assessed against the criteria specified in the Pfizer reporting standards. This assessment will consider whether each participant's baseline test results are within or outside the laboratory reference range for particular laboratory parameter.

Baseline will be the last pre-dose measurement. Change from baseline (CFB) will be calculated for all post-baseline timepoints.

3.1.3.2. Vital signs

Vital signs measures will include blood pressure (BP), pulse rate (PR), Temperature (Tympanic, Rectal or Skin), respiratory rate (RR) and Oxygen saturation (SpO₂). Baseline will be the last pre-dose measurement.

At times defined in the protocol SoA, a single measurement of BP and PR will be assessed with a completely automated device.

Temperature and the highest respiratory rate at the time of assessment will be recorded.

Oxygen saturation findings collected during the study will be recorded on the CRF including any supplemental O₂ requirement. The lowest SpO₂ value, while on room air at the time of assessment will be documented.

The following endpoints will be determined:

- Change from baseline in systolic and diastolic BP, pulse rate, temperature, respiratory rate, and SpO₂.
- The minimum and maximum post-dose systolic and diastolic BP, pulse rate, temperature, respiratory rate, and SpO₂.
- The maximum increase and decrease from baseline over all measurements taken post-dose for systolic and diastolic BP, pulse rate, temperature, respiratory rate, and SpO₂ values.

The maximum increase from baseline will be calculated by selecting the maximum CFB over the respective period, except in the case where a participant does not show an increase. In such an instance, the minimum decrease should be taken. Similarly, the maximum decrease from baseline will be determined by selecting the minimum value of the CFB. In cases where a participant does not show a decrease, the minimum increase should be taken.

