| Physical Examination (recorded in source document)   | X               | X                |                | X              | X              | X              |                | X                       | 
 
Day 1 complete physical exam pre-dose.
 
After Day 1, brief physical exam.
 
See Section 8.3.1.
 
See Appendix 10C in Section 10.10.3 for suggested chronology of assessments.
 
                                 |
| Body Weight  | X               |                  |                |                | X              |                | X              |                         | 
 
See Section 8.3.1.
 
  |
| Length / Head Circumference  | X               |                  |                |                |                |                |                |                         | 
 
See Section 8.3.1.
 
  |
| Vital signs including SpO 2   | X               | X                |                | X              | X              | X              |                | X                       | 
 
Before PK, NP swabs and IMP administration (See Appendix 10C in Section 10.10.3 for proposed chronology of assessment).
 
If hospitalized collect once daily until discharge and per SoA after discharge. See Section 8.3.2.
 
 |
| 12-Lead ECG  | X               |                  |                |                |                |                |                |                         | 
 
ECG may be performed after screening as needed per investigator discretion.
 
See Section 8.3.3 for ECG details.
 
See Appendix 10C in Section 10.10.3 for proposed chronology of assessment.
 
                         |
| Record Supplemental O 2 need  | X               | X                | X              | X              | X              | X              | X              | X                       | 
 
See Section 8.3.2.3.
 
  |

PFIZER CONFIDENTIAL

CT02-GSOP Clinical Protocol Template Phase 1 2 3 4 (14 April 2023)

Page 28

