| RSV-associated signs and symptoms (collected by HCP)                                       | X               | X                |         | X       | X       | X       |         | X                | 
 
Day 1 collected pre-dose.
 
Collected daily if hospitalized until time of discharge.
 
Collected if participant has an unplanned in person visit between Days CCI to CCI.
 
See Section 8.2.1.
 
   |
| Palatability assessment for oral dispersion through eDiary by parent(s)/legal guardian/HCP |                 | X                | X       | X       | X       |         |         |                  | 
 
Done after each dose.
 
See Appendix 10D in Section 10.10.4. Also see Section 8.2.2.
 
   |
| Explain eDiary   |                 | X                |         |         |         |         |         |                  | 
 
Explain eDiary completion requirements to participant's parent/legal guardian and assist with access to the eDiary (such as downloading the app or issue a provisioned device, if required).
 
  |

PFIZER CONFIDENTIAL

CT02-GSOP Clinical Protocol Template Phase 1 2 3 4 (14 April 2023)

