3.4.2. RSV Signs and Symptoms

RSV associated signs and symptoms will be assessed (as present/not present) by HCP (Appendix 10A of Protocol). The pre-dose assessment on Day 1 will be considered the baseline. Further assessments will be made over time with hospitalized patients assessed daily. Each sign and symptom will be analyzed separately.

Durations of RSV signs and symptoms at baseline will be determined. Duration at baseline is calculated as: baseline date – onset date + 1.

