5.2.2. Analyses for Binary/Categorical Endpoints

For binary or categorical endpoints, number of participants, numbers and percentages of participants meeting the categorical criteria will be presented in accordance with the sponsor reporting standards.

For the endpoints of signs and symptoms, a shift table of number of participants with and without a sign/symptom at Day [REDACTED] against baseline will be summarized for each sign/symptom separately. The proportion of participants with signs and symptoms will also be reported and plotted over time.

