6.1.3.2. Vital Signs

Absolute values and CFB in systolic and diastolic BP, pulse rate, temperature respiratory rate, and SpO₂ will be listed and summarized by cohort, age band, treatment and timepoint, according to sponsor reporting standards, using the safety analysis set defined in Section 4. Baseline is as defined in Section 3.1.3.2.

Mean absolute values and CFB for systolic and diastolic BP, pulse rate, temperature, respiratory rate, and SpO₂ will be plotted against time point. On each plot there will be one line for each cohort and age band with all treatments on the same plot. Corresponding individual plots of changes from baseline will also be produced for each treatment.

Maximum increase and decrease from baseline over all measurements taken post-dose for systolic and diastolic BPs, pulse rate, temperature respiratory rate, and SpO₂ will be summarized by cohort, age band and treatment, according to sponsor reporting standards.

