6.4.2. RSV Signs and Symptoms

A summary table will be presented to show the number and proportion of participants, by treatment, cohort and age band, with each sign/symptom of RSV listed in Appendix 10A of the protocol and RR and SpO₂, at each timepoint as described in Section 5.2.2.

In addition, shift tables will be presented by treatment, cohort and age band for each sign/symptom, at baseline and Day █ as described in Section 5.2.2.

Duration of the RSV signs and symptoms for each participant will be plotted using swimmer plots, with the x-axis ranging from the onset of symptoms prior to the start of the study or the start of the study, whichever is earlier.

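### Vital-sign extremes are taken over all post-dose readings, but inpatients are read daily and outpatients at three scheduled visits, so the summaries partly reflect care setting and length of stay

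*SAP*

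**What the plan says.** The trial enrols both outpatients and hospitalized children (SAP 2.3). For hospitalized children, the vital-signs row of the Schedule of Activities (Protocol Table 2) says: "If hospitalized collect once daily until discharge and per SoA after discharge". For everyone else the row marks Screening, Day 1, three later scheduled visits and early termination. Readings are to be taken "Before PK, NP swabs and IMP administration", so the Day 1 reading precedes the first dose.

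SAP 3.1.3.2, which falls under the primary endpoints, defines the minimum and maximum post-dose value and "The maximum increase and decrease from baseline over all measurements taken post-dose" for blood pressure, pulse rate, temperature, respiratory rate and SpO₂. SAP 6.1.3.2 then specifies the table: "Maximum increase and decrease from baseline over all measurements taken post-dose for systolic and diastolic BPs, pulse rate" and the other signs, by cohort, age band and treatment. Neither section limits the extremes to scheduled visits, reports the number of readings per child, or splits by care setting. SAP 6.5 plans no subset analyses. SAP 6.6.1 tabulates inpatient or outpatient status, but only at baseline.

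RSV signs and symptoms follow the same unequal schedule: "Collected daily if hospitalized until time of discharge" (Protocol Table 2) and "Further assessments will be made over time with hospitalized patients assessed daily" (SAP 3.4.2). SAP 5.2.2 adds: "The proportion of participants with signs and symptoms will also be reported and plotted over time". SAP 6.4.2 tabulates each sign "at each timepoint as described in Section 5.2.2".

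**The concern.** The expected maximum of a set of readings rises, and the expected minimum falls, as readings are added. A child read daily for a week will tend to show a larger greatest increase and a larger greatest decrease than an equally well child read three times. When such extremes are averaged by group, a group with more inpatients, or with longer stays, looks more variable without any drug effect.

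This matters because the primary objective compares safety with placebo, and the extremes are the only worst-value-per-child summary of vital signs in the current SAP 6.1.3.2. Protocol 6.3 describes allocation through the IRT system and does not mention stratification by care setting. Length of stay is also determined after randomization. Treatment could affect it, and Protocol 6.5 allows a stay to be prolonged for convenience. Age bands may differ in their share of inpatients, and randomization offers no protection for comparisons between them.

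**Working it through.** The documents give no figure to reproduce, so the size has to be worked out under stated assumptions.

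**From the documents.**
- Outpatient completer: 3 scheduled post-dose readings (Protocol Table 2).
- Inpatient: one reading a day until discharge, then the remaining scheduled visits.
- At most about 108 evaluable children (Protocol 9.5) over the 12 cohort and age-band cells listed in SAP 5.2: 108 / 12 = 9 per cell on average, both arms together.

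**Assumed.**
- The three scheduled visits fall on Days 3, 5 and 14 (the day labels are redacted).
- Daily readings start on Day 2, with discharge on Day 5, 7 or 10.
- Readings are normal with the same distribution in both settings, and day-to-day autocorrelation is 0, 0.5 or 0.7.

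**Step 1: number of readings, k.** For an inpatient, k counts the distinct days in Day 2 to discharge plus Days 3, 5 and 14. Discharge on Day 5 gives {2, 3, 4, 5, 14}, k = 5. Day 7 gives k = 7 and Day 10 gives k = 10.

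**Step 2: expected extreme.** A child's maximum increase is the child's maximum reading minus one baseline value. With the same baseline distribution in both settings, the baseline cancels from the gap, which equals E[max of k] − E[max of 3]. For independent readings, E[max of k] = ∫ x · k · φ(x) · Φ(x)^(k−1) dx and P(any reading above 2 SD) = 1 − Φ(2)^k. Units are within-child SD.

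| | k | E[max] | Gap from k = 3 | P(any > 2 SD) |
|---|---|---|---|---|
| Outpatient | 3 | 0.85 | – | 6.7% |
| Inpatient to Day 5 | 5 | 1.16 | 0.32 | 11% |
| Inpatient to Day 7 | 7 | 1.35 | 0.51 | 15% |
| Inpatient to Day 10 | 10 | 1.54 | 0.69 to 0.70 | 21% |

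The last gap is 0.69 from the integral and 0.70 by simulation.

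**Step 3: correlated readings (simulation).** For stays to Day 5 to 10, the gap is 0.22 to 0.58 SD at autocorrelation 0.5 and 0.16 to 0.47 SD at 0.7. Across all cases it is about 0.16 to 0.70 SD. By symmetry the same holds for the greatest decrease.

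**Step 4: shift between two groups.** Shift = gap × difference in inpatient share. With a difference of one third: 0.16 / 3 = 0.05 SD and 0.70 / 3 = 0.23 SD.

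**Step 5: how easily such an imbalance arises.** Arm sizes are redacted. Take a cell of 9 split 6:3, 7:2 or 5:4, with each child an inpatient independently with probability 30% to 70%. Binomial summation gives a 30% to 49% chance that the arms' inpatient shares differ by at least one third. With all 108 children pooled at an assumed 72:36 and 50% inpatients, the chance is about 0.1%.

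**Step 6: with common visits only.** Every child who completes has k = 3, so the gap due to reading frequency is zero by construction.

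**The case against.** The worst value over all post-dose readings is a reasonable choice for a safety summary, and limiting it to scheduled visits could drop a real excursion seen in hospital. That stands, and it is why the all-reading version should stay in the report.

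Randomization balances baseline setting in expectation, and Step 5 shows that chance imbalance almost disappears when cohorts are pooled. That also stands. It confines the problem mainly to single cells, to comparisons across age bands, and to length of stay after randomization.

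Other planned displays are largely unaffected. SAP 6.1.3.2 summarises and plots change from baseline by timepoint, and SAP 6.6.1 shows baseline setting by cohort, treatment and age band. These help a reader notice an imbalance, but they do not remove it from the extremes.

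A reader might infer that the primary safety comparison as a whole is biased. The documents do not support that. The primary endpoint is the incidence of clinically significant abnormal values, and the extremes are a supporting numerical summary. There are no hypotheses (SAP 5.1), and the interruption rules in Protocol 4.1.1 do not use the extremes.

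A reader might also infer that the symptom curves will jump on days when only inpatients are assessed. That cannot be established. The windows in SAP Appendix 1.1 are redacted after Day 1 and may pool or drop those days. SAP 5.2.2 already plans participant counts in the tables, and the baseline-to-fixed-day shift tables are largely unaffected. For the vital-sign extremes, visit windows are no remedy, because the definition takes in every post-dose reading.

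**Conclusion.** The concern holds for the vital-sign extremes, as a cheap improvement in interpretability and not as a threat to the trial's validity. The direction follows from how maxima and minima behave; the size in Steps 3 and 4 rests on assumed visit days, stays, correlations and inpatient shares. Equalising the reading schedule removes the artefact due to frequency. It does not remove any real difference in severity between inpatients and outpatients. For symptoms the concern is conditional on the redacted visit windows.

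**What to change.** In SAP 3.1.3.2 and 6.1.3.2, add maximum increase and maximum decrease derived only from the scheduled visits common to all children. State that this version is used for the comparison of sisunatovir with placebo. Keep the all-measurement extremes beside it, and show the number of readings per child.

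For symptoms, check the visit windows in SAP Appendix 1.1. If they allow days with only inpatients to appear as timepoints, limit the over-time proportions and plots in SAP 5.2.2 and 6.4.2 to the common scheduled visits. If they do not, nothing needs to change there.

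The cost is a few lines of SAP text, a data filter and one extra table. No new data are needed, and no safety information leaves the report.

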3.2. Secondary Endpoint(s)

3.2.1. Pharmacokinetic (PK) Endpoints

To calculate plasma concentrations of sisunatovir at steady state, blood samples will be taken on Day ^{cc} pre-dose, ^{CCI} post dose and pre dose on Day ^{cc}. If post-dose PK samples are not collected on Day ^{cc}, they will be collected on Day ^{cc}. For the purposes of plasma concentration summaries, the nominal day of the sample will be used.

3.3. Other Safety Endpoint(s)

Medical history and physical examination and neurological examination information, as applicable, collected during the course of the study, will be considered source data and will not be required to be reported, unless otherwise noted. However, any untoward findings identified on physical and/or neurological examinations conducted during the active collection period will be captured as AEs, if those findings meet the definition of an AE.

A single ECG will be collected at screening, and as specified in the SoA. ECG may be performed after screening as needed per investigator discretion. Any clinically significant ECG abnormalities that meet the definition of an AE will be captured as AEs.

3.4. Other Endpoint(s) (or, Exploratory Endpoints)

3.4.1. Viral Load

Viral load will be measured in NP swabs. Samples will be analyzed to measure RSV A and B RNA levels by reverse transcription polymerase chain reaction (RT-qPCR). For each participant and visit, the numeric viral load value will be the sum of that from subtype A and subtype B, followed by log₁₀ transformation for analysis.

Baseline will be measured pre-dose on Day 1. Change from baseline in viral load will be calculated at each sampled visit.

For viral load summaries, numeric log₁₀ copies/mL values will be derived from the possible categorical results as follows:

PFIZER CONFIDENTIAL

DMB02-GSOP-RF02 8.0 Statistical Analysis Plan Template

TMF Doc ID: 98.03

Page 9 of 20

- If the result is 'TND' (target not detected <LOD), a value of 0 \log_{10} copies/mL will be used, as applicable for both subtype A and B.
- If the result is 'TD' (target detected <LLOQ), the midpoint between the unlogged LLOQ and LOD will be used, ie, a value of 2.91 \log_{10} copies/mL will be used for subtype A (converted from a midpoint of 810 copies/mL) and 2.22 \log_{10} copies/mL for subtype B (converted from a midpoint of 165 copies/mL).
- If the result is '>ULOQ', a value of 9 \log_{10} copies/mL will be used, as applicable for both subtype A and B. Such values may ultimately be replaced by numeric results in subsequent data transfers.

Undetectable RSV viral load is defined as a central PCR laboratory result of 'TND' (or, a converted numeric value of 0 \log_{10} copies/ml) for both subtype A and subtype B.

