### **9.3.4. Tertiary/Exploratory Endpoint(s) Analysis**

Tertiary/Exploratory endpoints may not be reported in the CSR and may be reported separately. Descriptive summaries will be presented, if applicable. Further details will be provided in SAP.

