6.4. Other Endpoint(s) (or, Exploratory Endpoint[s])

6.4.1. Viral load

Absolute values and change from baseline in \log_{10} total RSV viral load by RT-qPCR will be summarized descriptively at each sampled visit by treatment, cohort, and age band, as described in Section 5.2.1. No imputation of missing data is planned. The absolute values and change from baseline in \log_{10} total RSV viral load by RT-qPCR at each timepoint will also be listed for each participant.

A spaghetti plot of viral load values over time (by visit) will also be produced, differentiating participants from each treatment group. The number and proportion of participants with TND and TD, RSV viral load at each sampled visit will be presented respectively by treatment, cohort, and age band as described in Section 5.2.2.

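### Does SAP 3.4.1 leave the total viral load open when neither RSV A nor RSV B is detected?

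*SAP*

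**What the plan says.** SAP 3.4.1 (Viral Load) builds the total from two subtype results: "the numeric viral load value will be the sum of that from subtype A and subtype B", and log10 is then taken of that sum. It then sets substitute values: "For viral load summaries, numeric log₁₀ copies/mL values will be derived from the possible categorical results as follows". By subtype these are:

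- Target not detected (TND): "If the result is 'TND' (target not detected <LOD), a value of 0" log10 copies/mL.
- Target detected below the quantification limit (TD): 2.91 log10 for A, from a midpoint of 810 copies/mL, and 2.22 log10 for B, from a midpoint of 165 copies/mL.
- Above the upper limit of quantification: 9 log10 for either subtype.

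The section ends by defining undetectable virus as TND, or "a converted numeric value of 0" log10, on both subtypes.

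SAP 6.4.1 uses the total for absolute values and change from baseline: log10 "total RSV viral load by RT-qPCR will be summarized descriptively at each sampled visit by treatment, cohort, and age band". It also provides a participant listing, a spaghetti plot, and counts of TND and TD at each visit. SAP 5.2.1 adds a geometric mean for variables analysed on a log scale. Protocol 9.3.4 says of this class of endpoint: "Tertiary/Exploratory endpoints may not be reported in the CSR".

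**The concern.** The substitute values are in log10 units, while the total is a sum that is logged only afterwards. The step between them, turning each code back into copies/mL, is not written. For most swabs this hardly matters. For a swab with TND on both subtypes, two totals can be argued. Back-transforming gives 1 + 1 = 2 copies/mL, or 0.30 log10. Reading the definition of undetectable as if it fixed the total gives 0.

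Two programmers could therefore assign the same swab totals 0.30 log10 apart. That difference would enter the visit mean, SD, minimum, listing and spaghetti plot, and also the median once at least half of a group is TND on both. Viral clearance is what a viral-load summary of an antiviral is meant to show, so such swabs can be expected after baseline. At stake is whether the summary could be reproduced from the SAP text alone.

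**Working it through.** **Inputs.** All codes are from SAP 3.4.1: TND = 0; TD = 2.91 (A) or 2.22 (B); above the upper limit = 9. The documents give no proportion of children TND on both subtypes and no baseline viral load. The 50%, the 20-point difference between arms and the baseline of 6 log10 used below are assumptions for illustration.

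**1. The plan's own figures.** log10(810) = 2.9085, which rounds to 2.91. log10(165) = 2.2175, which rounds to 2.22. Both reproduce, and they show that the codes stand for numbers of copies.

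**2. Which scale is summed.** With a and b the log10 codes for A and B, three literal readings are possible:

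| Swab (A / B) | log10(10^a + 10^b) | a + b | log10(a + b) |
|---|---|---|---|
| TND / TND | 0.301 | 0 | undefined |
| TD / TND | 2.911 | 2.91 | 0.464 |
| TND / TD | 2.223 | 2.22 | 0.346 |
| TD / TD | 2.991 | 5.13 | 0.710 |
| 6 (assumed) / TND | 6.000 | 6 | 0.778 |
| Above limit / above limit | 9.301 | 18 | 1.255 |

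Only the first column makes sense throughout. Adding the codes turns two results below quantification into 5.13 log10. Logging the sum of the codes turns 6 log10 into 0.778 and cannot be done for two TND results. The order in SAP 3.4.1, sum and then log, is the first column, and it gives 0.301 for TND on both.

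**3. Swabs with a detected subtype.** Counting the undetected subtype as 1 copy or as 0 copies changes the total by log10(811) − log10(810) = 0.0005 (A at TD) or log10(166) − log10(165) = 0.0026 (B at TD). Neither is visible in a summary.

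**4. Size where both are TND.** The difference per swab is 0.301 − 0 = 0.301. Let p be the proportion of children TND on both.

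- Visit mean: shift = 0.301 × p. This is 0.030 at p = 0.10, 0.151 at p = 0.50 and 0.301 at p = 1.
- Geometric mean: ratio = 2^p. This is 1.41 at p = 0.50 and 2 at p = 1.
- Difference between arms in the visit mean: 0.301 × 0.20 = 0.060 for an assumed 20-point difference in p.
- One child falling from an assumed 6 log10 to TND on both: −5.70 or −6.00.
- Mean change from baseline: shift = 0.301 × (p at the visit − p at baseline). A child TND on both at both times has change 0 under either rule. Baseline TND is possible: SAP 6.6.1 tabulates disagreements between the diagnostic test and the Day 1 swab, and Protocol 9.5 leaves replacement for Day 1 RNA below quantification to the sponsor's discretion.

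**5. Position on the scale.** The lowest code for a detected result is 2.22. The two candidates lie 2.22 − 0.30 = 1.92 and 2.22 − 0 = 2.22 log10 below it. The ordering of swabs is the same under either.

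**The case for a change.** The case for acting is that the gap is real and cheap to close. SAP 3.4.1 states no total for a swab that is TND on both, and SAP 5.3 and 6.4.1 supply none. The more firmly one accepts summing in copies/mL, the more firmly the total is 0.30, which sits awkwardly beside a definition of undetectable that uses 0. Change from baseline at each sampled visit is a listed endpoint in Protocol Section 3. SAP version 2 edited this section for clarity and added viral-load analyses, so a further sentence would have fitted that work.

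The observation about the text stands: the conversion and the total are not written. The inference that the derivation is open does not. The definition of undetectable classifies a swab by its two subtype results and assigns no total, so it does not compete with the stated sequence. Setting the total to 0 would be an exception to that sequence: an undetected subtype would count as 1 copy beside a detected one, while two undetected subtypes would together also count as 1. That is a preference between conventions. That two programmers would actually diverge is conjecture.

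The SAP abbreviation list includes a virology analysis plan that the visible text does not otherwise mention. Whether it holds more derivation detail cannot be told, and nothing here depends on it.

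**Conclusion.** No change to the plan follows. This is a missing detail that an analyst following the stated order fills without difficulty: convert to copies/mL, add A and B, take log10, and obtain 0.30 when both are TND.

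Even if 0 were used, a visit mean would move by 0.03 log10 per 10 percentage points of children TND on both, and by 0.30 at most. The mean change from baseline would move by 0.30 times the rise in that proportion since baseline. Either value is an arbitrary substitution well below anything detected, and a single program would apply it alike to both arms. The TND and TD proportions rest on the laboratory result and stay the same. The endpoint is tertiary and descriptive, no hypothesis is tested, and it may not appear in the clinical study report, so no conclusion turns on the choice.

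This rests on one rule being used for all swabs. The sizes at 50%, at a 20-point difference and from a baseline of 6 log10 are illustrations only.
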